- 9) Other concomitant drugs: drug name, reason for use, administration route, dose, and administration period
- 10) Drugs/combination therapies other than medication for ulcerative colitis

Presence or absence of drugs/combination therapies other than medication for ulcerative colitis, name of therapy, and therapeutic duration

11) Presence or absence of onset of tuberculosis or serious respiratory disorders

Examination day, imaging diagnostic method, abnormal findings, and abnormality

12) Mayo Score

Examination day (at initiation of administration, week 4, 8, 16, 24, 32, and 52 of administration, and discontinuation of administration)

13) CRP

Examination day (at initiation of administration, week 4, 8, 16, 24, 32, and 52 of administration, and discontinuation of administration)

14) Endoscopic finding

Examination day (at initiation of administration, week 24, 52 of administration, and discontinuation of administration)

15) Overall improvement (judgment by attending physician)

Judgment day (at week 52 of administration or at discontinuation)

Overall improvement (Remarkably effective, Effective, Ineffective, and Unevaluable)

16) Adverse events (including abnormal change in laboratory values)

Occurrence of adverse events, name of adverse events, onset day, seriousness, causal relationship to this drug, suspected drug(s), symptom and clinical course, treatment (with this drug or symptomatic treatment), outcome, laboratory values (if abnormally changed), and judgment reason if no causality

17) Key survey items

Infection, tuberculosis, malignant tumor, administration site reaction, autoimmune disease, pancytopenia, demyelinating disorders, congestive cardiac failure, and interstitial pneumonia

18) Measurement of anti-adalimumab antibody

If measurement of anti-adalimumab antibody is judged to be necessary

9. Analysis and Methods

- (1) Analytical items
 - 1) Patient population
 - 1. No. of enrolled patients
 - 2. No. of CRFs recovered
 - 3. Safety evaluation set
 - 4. Efficacy evaluation set
 - 2) Safety
 - 1. List of adverse reactions and infections
 - 2. Factors likely to affect the safety

- Incidence of adverse reactions by patient background
- Presence or absence of the use experience with anti-TNFα preparation and the relationship of safety.
- Safety in Long-Term administration
- Relationship of safety when anti-adalimumab antibody was determined
- Safety in patients conducting self-administration

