	(including surgery)" of the survey form, regard it as a prior treatment.
Dungan og/ohannon of	When prior-treatment data are contained in the survey form, it should
Presence/absence of prior treatment	be classified as "with prior treatment". When there is no description
	of "presence/absence of prior treatment" in the survey form or the
	assessment is impossible, it should be classified as "unknown/not
	provided", and other cases are "without prior treatment".
Draganaa/ahaanaa af	Surgery should be selected if the checkbox of prior treatment
Presence/absence of	(surgery) in "prior treatment for colitis ulcerative (including
prior treatment (surgery)	surgery)" is checked and if any prior treatment considered as surgery

Data name	Derivation and calculation methods
	is included in "[Humira UC] Conversion data provided for analysis".
	When the data applicable to surgery are contained, regard it as "with
	surgery". Others are "without surgery".
	If "leukocytapheresis" in "prior treatment (including surgery) for
Presence/absence of	colitis ulcerative" is checked and it is not applicable to with prior
prior treatment	treatment (surgery) in the survey form, it shall be classified into
(leukocytapheresis)	"with leukocytapheresis". Other cases are "without
	leukocytapheresis".
	If "enteral nutrition therapy" in "prior treatment (including surgery)
Presence/absence of	for colitis ulcerative" is checked and it is not applicable to with prior
prior treatment (enteral	treatment (surgery) in the survey form, it shall be classified into
nutrition therapy)	"with enteral nutrition therapy". Other cases are "without enteral
	nutrition therapy".
Presence/absence of	If "intravenous nutrition therapy" in "prior treatment (including
	surgery) for colitis ulcerative" is checked and it is not applicable to
prior treatment	with prior treatment (surgery) in the survey form, it shall be classified
(intravenous nutrition	into "with intravenous nutrition therapy". Other cases are "without
therapy)	intravenous nutrition therapy".
Presence/absence of	If "other therapy" in "prior treatment (including surgery) for colitis
	ulcerative" is checked and it is not applicable to with prior treatment
prior treatment (other	(surgery) in the survey form, it shall be classified into "with other
therapy)	therapy". Other cases are "without other therapy".
	Concomitant medications should the data satisfying the following
	rules: Note that when a drug code is null, it is not regarded as a

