	concomitant medication.
	When concomitant-medication data are contained in the survey form,
	it should be classified as "with concomitant medications". When
	there is no description of "presence/absence of prior/concomitant
Presence/absence of	medications" in the survey form or the assessment is impossible, it
concomitant medication	should be classified as "unknown/not provided", and other cases are
	"without concomitant medications".
	◆ Data with drug names in "the administration status of
	prior/concomitant medications for colitis ulcerative", "the
	administration status of other concomitant medication" of the survey
	form.

Data name	Derivation and calculation methods
Data name	 Derivation and calculation methods When the year and month are described for the first administration date of the concomitant medication, impute "1" for the "date". When the year is described for the first administration date of the concomitant medication, impute "1" each for the "month" and "date". When the year and month are described for the final administration date of the concomitant medication, impute the month's final date for the date. When the year is described for the final administration date of the concomitant medication, impute "12" for the month and "31" for the date. When the final administration of concomitant medication < the first administration date of Humira, and/or when the final administration date of Humira < the first administration date of concomitant medication. If the above imputing methods do not help add the date (the first administration date or the final administration date is not provided, etc.), or if the first administration date of concomitant medication are reversed, it should be regarded as a
	 Data with drug names in "priortreatment history for colitis ulcerative" of the survey form When the year and month are described for the first administration date of the prior medication, impute "1" for the "date". When the year is described for the final administration date of the prior medication, impute "1" each for the month and the date. If the final administration date of the prior medication ≥ the first administration date of Humira, regard it as a concomitant medication. If the above imputing methods do not help add the date, the final administration date of the prior medication shall be unknown and the case should not be regarded as a concomitant medication.

Data name	Derivation and calculation methods

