Presence/absence of concomitant medication (6-mercaptopurine) Presence/absence of concomitant medication	Refer to "171218 drug list_UC". If concomitant-medication data of the applicable drug code are provided in the survey form, regard the case as "with 6-mercaptopurine". Others are "without 6-mercaptopurine". Refer to "171218 drug list_UC". If concomitant-medication data of the applicable drug code are provided in the survey form, regard the
(azathioprine &	case as "with azathioprine & 6-mercaptopurine". Others are "without
6-mercaptopurine) Presence/absence of concomitant medication (tacrolimus & ciclosporin)	azathioprine & 6-mercaptopurine". Refer to "171218 drug list_UC". If concomitant-medication data of the applicable drug code are provided in the survey form, regard the case as "with tacrolimus & ciclosporin". Others are "without tacrolimus & ciclosporin".
Presence/absence of	Refer to "171218 drug list UC". If concomitant-medication data of
concomitant medication (antibiotics)	the applicable drug code are provided in the survey form, regard the case as "with antibiotics". Others are "without antibiotics".
Presence/absence of concomitant medication (others)	When concomitant-medication data on the drug code applicable to the drug other than aminosalicylic acid drug, corticosteroids, azathioprine, 6-mercaptopurine, tacrolimus, ciclosporin and antibiotics are included in reference to "171218 drug list_UC", regard it as "with others". Other cases are "without others".
Presence/absence of administration of anti-hepatitis B virus agent	If the following drug codes are included in the survey form, regard the case as "with administration of an anti-hepatitis B virus agent". Others are "without administration of an anti-hepatitis B virus agent". Entecavir (Baraclude): 6250029 Tenofovir (Tenozet, Viread): 6250024 Adefovir (Hepsera): 6250026 Lamivudine: 6250006, 6250020
Presence/absence of concomitant therapy	It should be described in "non-medicinal treatment/concomitant therapy (including surgery) for colitis ulcerative" of the survey form. The data from the first administration date to the final administration date of Humira will be calculated. Such data are also subject to calculation even if the first/final administration dates of concomitant treatment are not unknown. (Only when the days are not overlapped with the administration

Data name	Derivation and calculation methods
	period of Humira, they shall be excluded from the calculation.) When

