	concomitant-therapy data are contained in the survey form, it should
	be classified as "with concomitant therapy". When "presence/absence
	of prior/concomitant medications" is not provided in the survey form
	or the assessment is impossible, it should be classified as
	"unknown/not provided", and other cases are "without concomitant
	therapy".
	Surgery should be selected when the 'surgery' checkbox of
	non-medicinal treatment/concomitant therapy name is checked in
D /1 C	"non-medicinal treatment/concomitant therapy for colitis ulcerative
Presence/absence of	(including surgery)" and when any concomitant therapy considered
concomitant therapy	as surgery is included in "[Humira UC] Conversion data provided for
(surgery)	analysis".
	When the data applicable to surgery are contained, regard it as "with
	surgery". Others are "without surgery".
	If "leukocytapheresis" in "non-medicinal treatment/concomitant
Presence/absence of	therapy (including surgery) for colitis ulcerative" is checked and it is
concomitant therapy	not applicable to with concomitant therapy (surgery) in the survey
(leukocytapheresis)	form, it shall be classified into "with leukocytapheresis". Other cases
	are "no leukocytapheresis".
	If "enteral nutrition therapy" in "non-medicinal
Presence/absence of	treatment/concomitant therapy (including surgery) for colitis
concomitant therapy	ulcerative" is checked and it is not applicable to with concomitant
(enteral nutrition	therapy (surgery) in the survey form, it shall be classified into "with
therapy)	enteral nutrition therapy". Other cases are "no enteral nutrition
	therapy".
	If "intravenous nutrition therapy" in "non-medicinal
Presence/absence of	treatment/concomitant therapy (including surgery) for colitis
concomitant therapy	ulcerative" is checked and it is not applicable to with concomitant
(intravenous nutrition	therapy (surgery) in the survey form, it shall be classified into "with
therapy)	intravenous nutrition therapy". Other cases are "no intravenous
	nutrition therapy".
Presence/absence of	If "other therapy" in "non-medicinal treatment/concomitant therapy
concomitant therapy	(including surgery) for colitis ulcerative" is checked and it is not
(other therapy)	applicable to with concomitant therapy (surgery) in the survey form,
(other therapy)	it shall be classified into "with other therapy". Other cases are "no

Data name	Derivation and calculation methods
	other therapy".

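### Two derivation rules in SAP 10.1 are wrong as written: unknown concomitant therapy is keyed to the medications question, and month-year stop dates of prior-history drugs have no completion rule

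*SAP*

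**What the plan says.** **(a) Concomitant therapy.** SAP 10.1 names the source of the variable: "It should be described in 'non-medicinal treatment/concomitant therapy (including surgery) for colitis ulcerative' of the survey form". Patients with data there are classed as having concomitant therapy. The class 'unknown/not provided' is assigned when the presence or absence "of prior/concomitant medications' is not provided in the survey form", or when assessment is impossible. Everyone else is 'without'. Two other entries in the same section serve for comparison:

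- The concomitant-medication rule uses the same trigger: "there is no description of 'presence/absence of prior/concomitant" medications.
- The prior-treatment rule has its own trigger, a missing description "of 'presence/absence of prior treatment' in the survey form or the" assessment being impossible.

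Protocol 8(3) item 10 lists a separate data item for therapies: "Presence or absence of drugs/combination therapies other than medication for ulcerative colitis, name of therapy, and therapeutic duration".

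**(b) Drugs in the prior-treatment history.** Under concomitant medication, SAP 10.1 counts such a drug as concomitant if its final date is on or after the first Humira date. Two completion rules come before that test:

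- "When the year and month are described for the first administration date of the prior medication", the day is set to 1.
- "When the year is described for the final administration date of the prior medication", month and day are both set to 1.

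If these do not yield a date, "the final administration date of the prior medication shall be unknown and the case should not be regarded as a concomitant medication".

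**The concern.** In (a), the unknown class of one variable is set by the answer to a different question. Missing therapy information can then be reported as no therapy, and a clear 'no' can be reported as unknown. Under SAP 9.5 unknowns leave the statistical test, while under SAP 9.2 they stay in the percentage denominator.

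In (b), the month-year rule completes a date that the decision never uses, and the date that it does use has no month-year rule. A drug that certainly overlapped Humira treatment can be analysed as if it had not. Unlike in (a), the patient stays in the test on the wrong side, because the individual drug-class factors have no unknown category.

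The variables are background factors in charts 2.9 and 3.4, and in 3.4.1, which takes its list from 3.4. Factors affecting safety and effectiveness are a stated aim of the survey, and significance in 2.9 decides which 2.9.xx breakdowns are produced.

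**Working it through.** The plan states no figure here, so there is none to reproduce. The check applies each rule as written and as it would read if corrected.

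**(a)** Inputs are whether therapy data exist, whether the therapy question is answered, and whether the medications question is answered. With therapy data present, both rules give 'with' in all four combinations. Without therapy data:

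| Therapy question | Medications question | As written | Using the therapy question |
|---|---|---|---|
| no | answered | without | without |
| no | blank | unknown | without |
| blank | answered | without* | unknown |
| blank | blank | unknown | unknown |

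*Unless the clause on impossible assessment is taken to cover it.

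Two of the four combinations differ. The surgery, leukocytapheresis and nutrition sub-factors do not change, because they have no unknown class.

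**(b)** The test is: stop date ≥ first Humira date. Take Humira started on 1 June 2015.

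| Recorded stop | Completed as written | Result as written | Day 1 rule | Month-end rule |
|---|---|---|---|---|
| 2015-08 | no rule | not concomitant | 1 Aug 2015, concomitant | 31 Aug 2015, concomitant |
| 2015 | 1 Jan 2015 | not concomitant | – | – |
| 2016-02 | no rule | not concomitant | 1 Feb 2016, concomitant | 29 Feb 2016, concomitant |
| 2016 | 1 Jan 2016 | concomitant | – | – |

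The year-only line cannot stand in for the missing rule: it supplies the month as well as the day, and here the month is already recorded. So no month-year stop in this section can qualify under the written text.

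The like-for-like comparisons are 2015-08 with 2015, and 2016-02 with 2016. In the first pair both forms fail. In the second the vaguer form qualifies and the more precise one does not. That reversal needs a stop in a later calendar year than the Humira start.

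The other date rules in SAP 10.1, for concomitant drugs and anti-tuberculosis drugs, complete month-year and year-only dates for both start and stop. The gap exists only in the prior-history block.

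**Choice of completion day.** Assume every Humira start from July 2013 to July 2016, true stops spread evenly from 90 days before to 364 days after the start, and all stops recorded as month-year. The share of truly overlapping drugs counted as concomitant is 0% as written, 96% with day 1 and 100% with month end. Of stops in the 90 days before the start, day 1 counts none as concomitant and month end counts about 16%. These shares depend on the assumed spread and are not estimates for this survey.

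**The case against.** Four points can be made against this.

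1. The clause on impossible assessment in the therapy rule may be meant to catch a blank therapy question. That is possible, but the SAP does not say so. It also leaves the opposite error untouched, where therapy is answered 'no' and the medications question is blank. The case report form is not among the documents, so the exact layout of its questions cannot be checked.

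2. Rule (b) reads the correct field in its decision step, and naming the start date in the month-year line looks like a one-word slip, perhaps from translation. Whether programming followed the slip cannot be known. The written text still needs the correction.

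3. A reader might infer that any drug with a stop month after the first Humira dose is lost. The documents do not support that. Protocol 8(3) item 4 limits prior medications to the 3 months before Humira, and item 8 collects concomitant drugs for ulcerative colitis separately. SAP 10.1 handles that separate section with complete date rules and, where dates are missing, defaults to concomitant. Only a drug entered solely in the prior history is exposed.

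4. A reader might also infer that more precise dates generally give the worse classification. As the date table shows, that holds only across a calendar-year boundary.

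The variables feed unadjusted single-factor tests over a long list of factors in a single-arm survey. The overall incidence and remission estimates do not use them. This keeps the severity low but does not make either rule right.

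**Conclusion.** Both rules are wrong as written, and the point is minor. In (a), only the overall concomitant-treatment factor is affected, and only patients without therapy data can move, between 'without' and 'unknown'. In (b), the error runs one way, from concomitant to not concomitant, and only for drugs recorded solely in the prior-treatment history with a month-year stop date. The documents give no counts of blank answers or partial dates, so the number of patients misclassified cannot be stated and could be small. The conclusion assumes that the SAP text is what was programmed and that the form carries a therapy presence/absence answer, as Protocol 8(3) item 10 indicates.

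**What to change.** (a) In the concomitant-therapy rule, set 'unknown/not provided' from the presence/absence item for non-medicinal treatment/concomitant therapy, and not from the medications question.

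(b) In the prior-history block, make the month-year rule apply to the final date. Keeping day 1 matches the existing year-only rule for that date; month end would match the rule for concomitant drugs. State one of the two and apply it to every month-year stop date, including stops in the month of the first Humira dose, with no separate fallback for those.

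Then re-run both derivations and charts 2.9, 3.4 and 3.4.1, plus any 2.9.xx table whose selection changes. Chart 1.12 tabulates the same factors and should be refreshed with them. The cost is two wording changes and two derivations, with no new data. Reporting how many patients change class would show whether the correction matters.

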Sex, pregnancy/nursing, race, age (year), body weight (kg), BMI (kg/m²), duration of illness (year), indication (registration form), allergy history, smoking history, detailed classification of smoking history, tuberculosis test, hepatitis B test, complication, detailed classification of complications, complication/others, medical history, detailed classification of medical history, prior medication for colitis ulcerative, detailed classification of prior medication for colitis ulcerative, treatment for colitis ulcerative, detailed classification of medical product, concomitant medication for colitis ulcerative, detailed classification of "with" biological product, concomitant medication for colitis ulcerative, detailed classification of concomitant medication for colitis ulcerative, concomitant treatment for colitis ulcerative, detailed classification of the disease site "colon", site of disease by type, partial Mayo score, CRP

Note: For the discontinuation reasons for the detailed classification of pregnant/nursing or 'using' biological products", calculate the percentage to the aggregation item right above the item. For other items, calculate the percentage to the number of target patients.

Overlapped aggregation may occur in the detailed classification of complications and complication of other classification, detailed classification of medical history, detailed classification of prior medications for colitis ulcerative, detailed classification of prior treatment for colitis ulcerative, detailed classification of 'using' biological products', detailed classification of concomitant medications for colitis ulcerative, detailed classification of concomitant treatment for colitis ulcerative, and the detailed classification of site of disease for colitis ulcerative and the site of

disease "colon".

"1.13 Incidence of self-administration error"

Patients for analysis: patients in the safety analysis group

Analysis objective: to show the distribution status for presence/absence of self-administration and the detailed classification of self-administration.

Analysis item: calculate the number of patients in the analysis groups.

Calculate the number of patients per "self-administration" defined in "11. How to stratify data" and the percentage to the number of patients in the analysis groups.

In addition, calculate the number of patients per "self-administration error" and the percentage to the patients 'with' self-administration.

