Age (year), the elderly, pediatrics, sex, body weight (kg), BMI (kg/m²), duration of illness (year), complications, complication: hepatic function disorder, complication; renal impairment, complication: blood disorder, complication: respiratory disorder, complication: diabetes mellitus, complication: osteoporosis, complication: malignant tumour, medical history, medical history: tuberculosis, medical history: non-tuberculous mycobacteriosis, medical history: interstitial pneumonia, medical history: bronchitis bacterial, medical history: aplastic anaemia, medical history: pancytopenia, medical history: malignant tumour, allergy history, smoking history, detailed history of smoking history, the administration status of Humira: self-administration, prior medication, prior medication: biological product, prior medication Infliximab, prior medication: other biological product, prior medication: aminosalicylic acid drug, prior medication: corticosteroids, prior medication: azathioprine, prior medication 6-mercaptopurine, prior medication: azathioprine & 6-mercaptopurine, prior medication: tacrolimus & ciclosporin, prior treatment, prior treatment: leukocytapheresis, prior treatment: surgery, prior treatment: enteral nutrition therapy, prior treatment: intravenous nutrition therapy, concomitant medication, concomitant medication: aminosalicylic acid drug, concomitant medication: corticosteroids, concomitant medication: azathioprine, concomitant medication: 6-mercaptopurine, concomitant medication: azathioprine & 6-mercaptopurine, concomitant medication: tacrolimus & ciclosporin, concomitant treatment, concomitant treatment: leukocytapheresis, concomitant treatment: surgery, concomitant treatment: intravenous nutrition therapy, concomitant treatment: enteral nutrition therapy, site of disease by type, partial Mayo score, CRP

"2.9.xx Incidence of adverse reactions per background factor and seriousness"

Patients for analysis: patients in the safety analysis group

Analysis objective: to show the onset status of non-serious/serious adverse reactions per statistically-significant background factor based on the test results in 2.9.

Analysis item: aggregate the following items per background factor and seriousness for adverse reactions which occurred in the safety analysis period.

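### As worded, the surgery exclusion in SAP 10.1 codes patients who had both surgery and another non-drug therapy as 'without' that therapy, and 'unknown' for concomitant therapy is keyed to the wrong question

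*SAP*

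**What the plan says.** For concomitant therapy, SAP 10.1 sets two conditions for leukocytapheresis. The box under "therapy (including surgery) for colitis ulcerative' is checked and it is" also required to be "not applicable to with concomitant therapy (surgery) in the survey" form. The outcome is two-way: "form, it shall be classified into 'with leukocytapheresis'. Other cases" are coded as no leukocytapheresis. Enteral nutrition, intravenous nutrition and other therapy follow the same pattern. The four prior-treatment definitions in the same section repeat it: the box "is checked and it is not applicable to with prior" treatment (surgery). None of these eight variables has an unknown or excluded level.

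Surgery itself is identified from its own checkbox and from entries judged to be surgery in a separate conversion file.

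The note to Table 1.12 (SAP 13.1) begins "Overlapped aggregation may occur in the detailed classification of complications and complication of other classification" and goes on to list the detailed classifications of prior and concomitant treatment, with no exception for surgery.

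Table 2.9 (SAP 13.2) tests leukocytapheresis, surgery, enteral nutrition and intravenous nutrition as separate factors, prior and concomitant; one entry reads "concomitant treatment: intravenous nutrition therapy". Table 3.4 has the same list and Table 3.4.1 reuses it.

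For the overall concomitant-therapy variable, the unknown category applies when the presence or absence "of prior/concomitant medications' is not provided in the survey form", or when assessment is impossible. The matching prior-treatment variable is keyed to the prior-treatment question.

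**The concern.** The survey's third objective is to find factors that affect safety and effectiveness. If the surgery condition works on the patient, a form that records both surgery and intravenous nutrition gives a patient coded as never having had intravenous nutrition. The error is not random. It touches only patients with both treatments and always moves them to 'without', so that group holds every surgery patient and the 'with' group holds none. If surgery is related to outcome, the comparison for the other therapy is distorted.

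The affected rows feed Fisher's exact tests at the two-sided 5% level (SAP 9.6). Significance in Table 2.9 also decides which factors get a further breakdown in Table 2.9.xx. The frequencies in Table 1.12 would be too low for all eight therapy rows.

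The unknown rule is a second, smaller problem. SAP 9.5 keeps unknowns out of the tests and SAP 11 gives concomitant therapy an unknown level, but the trigger for that level is a question about drugs.

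**Working it through.** **1. The rule as a truth table (patient-level reading).**

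| Therapy box | Surgery | Coded | Correct |
|---|---|---|---|
| no | no | without | without |
| no | yes | without | without |
| yes | no | with | with |
| yes | yes | **without** | **with** |

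Only the last row is wrong.

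**2. Which reading do the passages support?** The exclusion refers to the surgery variable defined just above it, which labels a case as with surgery. SAP 10.1 uses the parallel label for prior infliximab at case level when it builds the biologics history. The named drug-class definitions in the same section contain no mutual exclusion. These points favour the patient level. The Table 1.12 note points the other way: if the exclusion works per patient, surgery can never overlap with the other therapies. Overlap among the non-surgical therapies would remain possible, so this is tension and not strict contradiction.

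**3. Rows affected.** Three therapies (leukocytapheresis, enteral nutrition, intravenous nutrition) × two periods (prior, concomitant) = 6 tested factors. Other therapy × two periods = 2 further rows, tabulated in Table 1.12 only.

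**4. How many patients move.** Moved = N × P(therapy) × P(surgery | therapy). N = 1500 is the target in SAP 4.3. The documents give neither probability, so these are assumptions: therapy use 5–30%, surgery among users 2–40%.
- Low end: 1500 × 0.05 × 0.02 = 1.5
- High end: 1500 × 0.30 × 0.40 = 180
- At 10% use: 3, 15 and 60 patients for 2%, 10% and 40% overlap

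**5. Effect on the comparison.** All rates are assumed. Take 10% therapy use (150 users, 1350 non-users) and surgery in 2% of non-users. With m patients moved:

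coded 'without' rate = (1350 × non-user rate + m × rate in those moved) / (1350 + m)

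(a) Surgery unrelated to outcome; adverse reactions in 30% of users and 20% of non-users; m = 15. True difference +10.0 points. Coded 'without' = (270 + 4.5)/1365 = 20.1%, difference +9.9.

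(b) Adverse reactions in 50% of surgery patients, otherwise as (a). Non-user rate = 0.98 × 20% + 0.02 × 50% = 20.6%.
- 10% overlap: true 32.0% − 20.6% = +11.4. Coded 'without' = (278.1 + 7.5)/1365 = 20.9%, difference +9.1.
- 40% overlap: true 38.0% − 20.6% = +17.4. Coded 'without' = (278.1 + 30)/1410 = 21.9%, difference +8.1.

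(c) Effectiveness 60% with neither, 50% with therapy only, 10% with surgery. Non-user rate = 0.98 × 60% + 0.02 × 10% = 59.0%.
- 10% overlap: true 46.0% − 59.0% = −13.0. Coded 'without' = (796.5 + 1.5)/1365 = 58.5%, difference −8.5.
- 40% overlap: true 34.0% − 59.0% = −25.0. Coded 'without' = (796.5 + 6)/1410 = 56.9%, difference −6.9.

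At 2% overlap the shift is below 1 point in all three. At the far end of the range (30% use, 40% overlap), case (c) goes from −25.0 to −1.8: (1050 × 59.0% + 180 × 10%)/1230 = 637.5/1230 = 51.8%, and 50.0% − 51.8% = −1.8.

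**6. The unknown key.** Medication question answered, therapy question blank: 'without', unless assessment is held to be impossible. Medication question blank, therapy question answered no: 'unknown'. Both are the reverse of what the form shows.

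**The case against.** The strongest reply is that the exclusion works on the single entry. Protocol section 8 collects non-drug therapies by name and duration, SAP 10.1 selects them by date overlap with Humira, and surgery is assigned partly through recoding. The clause may then only stop an entry recoded as surgery from being counted again under its old name. The Table 1.12 note fits this better, and neither the survey form nor the conversion file is available to check it. This stands as a possible intention. It does not settle the matter, because the text says nothing about entries, and the clause would have little to do for a ticked leukocytapheresis or nutrition box.

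A second reply is that these are exploratory single-factor tests and that surgery has its own row. A crude comparison that includes surgery patients is also confounded. In case (b) the coded +9.1 lies nearer to the +10.0 among non-surgical patients than the crude +11.4 does. That is fair, but the coded contrast is neither of those quantities: it keeps surgery patients on one side only. In case (c) it falls short of both the crude difference and the −10.0 among non-surgical patients.

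A reader might infer that associations are reversed. That can be constructed: with 300 intravenous nutrition users, 27 of whom are among 30 surgery patients, and reaction rates of 60% with surgery and 20% otherwise, 23.6% v 20.1% becomes 20.0% v 21.0%. But the therapy has no effect within either stratum there, and with whole-patient counts Fisher's test gives p = 0.18 (71/300 v 241/1200) and p = 0.81 (55/273 v 257/1227). Reversal is not shown.

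**Conclusion.** The point holds in a limited form. Followed literally, the wording miscodes patients who had both surgery and another listed therapy, and the SAP does not state the entry-level rule that would avoid this. Six tested factors can be biased and two descriptive rows affected.

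The size is unknown. Under the assumed ranges it runs from 0.1 point or less to a loss of more than 20 points. The large values need both substantial overlap and a strong link between surgery and outcome, and the documents give no figure for either.

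A reader might go further and conclude that every surgery patient is miscoded, that the factor results are wrong, or that the sickest patients are moved. The documents do not support this: surgery-only patients are coded correctly, error in the results depends on unknown quantities, and the SAP holds no severity data on these patients.

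The unknown key is a separate slip. It concerns only the overall concomitant-therapy variable, which is itself a tested factor. Its effect cannot be sized from the documents.

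**What to change.** - In SAP 10.1, remove the surgery condition from the leukocytapheresis, enteral nutrition, intravenous nutrition and other-therapy definitions, prior and concomitant, and code each from its own checkbox whatever the surgery status. If recoding was the intention, state instead that only the individual record recoded as surgery is moved and that the patient's other records stay.
- Key 'unknown/not provided' for concomitant therapy to the question on non-medicinal treatment and concomitant therapy, in line with the prior-treatment rule.
- Report the number of patients with both surgery and each other therapy, so that readers can judge the overlap.

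The cost is a few lines of SAP wording and code, with a rerun of Tables 1.12, 2.9, 2.9.xx, 3.4 and 3.4.1 if they have already been produced. No new data are needed.
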